8.4 TREATMENT OF OVERDOSE

Study treatment overdose is the accidental administration of a drug in a quantity that is higher than the assigned dose. An overdose or incorrect administration of study treatment is not an adverse event unless it results in untoward medical effects (see Sections 5 and 5.2 of [Appendix 2](#) for further details).

In the event of an overdose, the Investigator should:

1. Contact the Sponsor's Medical Monitor immediately.
2. Closely monitor the participant for AE/SAE and laboratory abnormalities until resolved.
3. Obtain blood samples for PK analysis according to the schedule of assessments if not medically contraindicated.
4. Document the quantity of the excess dose, as well as the duration of the overdose, in the CRF.

8.5 LUMBAR PUNCTURES

■ lumbar punctures per participant will be performed at the times indicated in the SoA (see Section 1.3) to collect CSF, performed by a qualified physician. Atraumatic needles will be used, the liquid will be sampled in a free flowing manner, which will take about 5 minutes. For details please see the Laboratory Manual

CSF Samples will be aliquoted per time point for the measurement of RO7126209 (Section 8.6.1), ■

■
Details on processes for collection and shipment of these samples can be found in Sample Handling Manual.

8.6 PHARMACOKINETICS

As a general note, any volume of blood or CSF samples remaining after the specified analyses may be used for assay development/validation of exploratory assays and experiments. In addition, blood samples may be used to measure levels of total binding competent gantenerumab, characterize drug molecule integrity and potential soluble target interference. If performed, the results will be reported in a separate report to the CSR.

Any changes in the timing or addition of time-points for any planned study assessments must be documented and approved by the relevant study team member and then, archived in the Sponsor and site study files, but this will not constitute a protocol amendment.

Placebo-treated participants may not be analysed in the first instance, but retained for subsequent analysis if appropriate.

The PK blood and CSF samples will be destroyed 6 months after the release of final bioanalytical report at the CRO performing the analysis or shipped to Roche. In the latter case the samples may be stored up to 2 years after the date of final CSR. Details on sampling procedures, sample storage and shipment are given in the sample documentation.

8.6.1 Plasma

Mandatory blood samples to evaluate concentrations of RO7126209 in plasma will be collected as outlined in the SoA (see Section 1.3).

Blood samples must not be taken from the same arm as IV drug administration on Day 1. The date and time of each sample collection will be recorded in the eCRF.

Plasma concentrations of RO7126209 will be measured by a specific and validated [REDACTED] method. PK parameters will be estimated using standard non-compartmental methods.

During the course of the study, number of samples and PK sampling time-points may be modified on the basis of emerging data to ensure the pharmacokinetics of RO7126209 can be adequately characterized.

8.6.2 Cerebrospinal Fluid

CSF samples will be collected at the timepoints outlined in the SoA (Section 1.3) and as described in Section 8.5.

RO7126209 CSF concentrations will be measured by a specific and validated [REDACTED] method. CSF pharmacokinetic data will not be required for dose escalation decision.

8.7 IMMUNOGENICITY ASSESSMENTS

As RO7126209 is a bispecific monoclonal antibody there is a risk that ADA against RO7126209 could develop, potentially reducing its efficacy and/or potentially resulting in symptomatic hypersensitivity reaction, including immune-complex reactions. Antibodies to RO7126209 will be evaluated in blood samples collected from all participants according to the SoA (Section 1.3). ADA data will not be required for dose escalation decisions.

[REDACTED]

[REDACTED]

[REDACTED]. The date and time of each sample will be recorded in the eCRF.

[REDACTED]

The blood samples will be destroyed 6 months after the release of final bioanalytical report at the CRO performing the analysis or shipped to Roche. In the latter case the samples may be stored up to 2 years after the date of final CSR. Details on sampling procedures, sample storage and shipment are given in the sample documentation.
Details on sampling procedures, sample storage and shipment are described in the sample documentation.

8.8 PHARMACODYNAMICS AND BIOMARKER ANALYSES

8.8.1 Biomarker Research Sample

CSF samples will be collected and aliquoted before and after study drug administration as described in the SoA (Section 1.3) and Section 8.5. [REDACTED]

[REDACTED]

The samples may also be used for research purposes to identify biomarkers useful for predicting and monitoring response to study treatment, identifying biomarkers useful for predicting and monitoring study treatment safety, assessing pharmacodynamic effects of study treatment, and investigating mechanism of therapy resistance. Additional markers may be measured in the case that a strong scientific rationale develops.

Unless otherwise specified below, samples will be destroyed no later than 5 years after the date of final CSR.

8.8.2 Clinical Genotyping

APOE ε4:

In case of occurrence of ARIA, a whole blood sample will be obtained for DNA extraction. These participants will be evaluated for APOE ε4 genotype in order to identify their status with respect to their known risk factors for ARIA.

Data arising from these analyses will be subject to the same confidentiality as the rest of the study.

The residual blood will be destroyed within 5 years after the date of final closure of the final CSR.

Details on processes for collection and shipment of these samples can be found in the Sample Handling Manual.

8.9 HEALTH ECONOMICS

Health Economics/Medical Resource Utilization and Health Economics parameters will not be evaluated in this study.

8.10 TIMING OF STUDY ASSESSMENTS

8.10.1 Order of Assessments

At timepoints where more than one assessment is required, the following sequence should be followed as applicable, and priority will be given to the PK blood sample being taken at the scheduled time: (1) ECGs; (2) Vital signs; (3) Respiratory rate; (4) PK blood sampling; (5) Laboratory safety tests and other blood sampling (anti-RO7126209 antibodies); (6) CSF sampling; (7) others.

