1.3 SCHEDULE OF ACTIVITIES

The schedule of the activities is provided in [Table 1](#) and [Table 2](#).

Table 1 Overall Schedule of Activities

Assessment	Screening ^a																Follow-Up
	Day -56/-3	Day -2	Day -1	Day 1	Day 2	Day 3	Day 4	Day 5	Day 6	Day 7	Day 8	Day 10	Day 15±1	Day 22±1	Day 29±2	Day 43±3	Day 57±4
Time relative to dose (h)	NA	NA	NA	0	24	48	72	96	120	144	168	NA	NA	NA	NA	NA	NA
Written Informed Consent	✓																
Inclusion/Exclusion Criteria	✓	✓															
Brain MRI ^l	✓									✓							✓
Demographics	✓																
Medical History	✓																
Medication History	✓	✓															
Physical Examination ^b	✓	✓															✓
Vital Signs ^c	✓	✓		✓	✓	✓	✓	✓	✓	✓	✓	✓	✓		✓	✓	✓
Respiratory rate ^j		✓		✓	✓	✓					✓						
12-lead ECG ^d	✓	✓		✓	✓		✓		✓		✓	✓	✓		✓	✓	✓
Neurological Examination	✓	✓		✓	✓	✓	✓		✓		✓		✓		✓		✓
Full hematology	✓	✓			✓			✓			✓		✓		✓		✓
Full Blood	✓ ^q	✓			✓						✓		✓		✓		✓

Assessment	Screening ^a																Follow-Up
	Day -56/-3	Day -2	Day -1	Day 1	Day 2	Day 3	Day 4	Day 5	Day 6	Day 7	Day 8	Day 10	Day 15±1	Day 22±1	Day 29±2	Day 43±3	Day 57±4
Time relative to dose (h)	NA	NA	NA	0	24	48	72	96	120	144	168	NA	NA	NA	NA	NA	NA
Chemistry																	
Urinalysis ^e	✓	✓			✓		✓						✓		✓		✓
Serology ^f	✓																
Cerebral spinal fluid			✓ ⁿ			✓ ^o		✓ ^o									
Coagulation	✓	✓				✓ ^o		✓ ^o									✓
Alcohol Test	✓	✓															
Drugs of Abuse	✓	✓															
In-house Period		←----->															
Randomization				✓													
Standard Meal ^g		✓	✓	✓	✓	✓	✓	✓	✓	✓	✓	✓					
Drug Administration				✓													
Pharmacokinetic				✓	✓	✓	✓	✓			✓	✓	✓	✓	✓	✓	✓

Assessment	Screening ^a																Follow-Up
	Day -56/-3	Day -2	Day -1	Day 1	Day 2	Day 3	Day 4	Day 5	Day 6	Day 7	Day 8	Day 10	Day 15±1	Day 22±1	Day 29±2	Day 43±3	Day 57±4
Time relative to dose (h)	NA	NA	NA	0	24	48	72	96	120	144	168	NA	NA	NA	NA	NA	NA
Sampling (Blood) ⁱ																	
Infusion-related reaction blood sample				✓	←-----→												
Previous and concomitant Medications	←-----→																
Adverse Events ^h	←-----→																
Anti-RO7126209 Antibodies				✓							✓					✓	✓ ^p

- a) Safety tests can be repeated once during screening period at discretion of the Investigator.
- b) A complete physical examination will be performed at screening (including height and weight), and abbreviated physical examinations at all other visits (including weight).

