- c) Includes single measurements of systolic and diastolic blood pressure, pulse rate and body temperature. All measurements to be taken after the participant has rested in a supine position for at least 5 minutes.
- d) Triplicate 12-lead ECGs (within 5 minutes) will be measured after the participant has rested in a supine position for at least 10 minutes.
- e) Dipstick analysis of protein, blood, glucose, pH and leukocytes.
- f) Hepatitis B, C, HIV 1 and 2.

Table 1 Overall Schedule of Activities (cont.)

- g) Participants will have to be fasted (water consumption is permitted) for at least 10 hours prior to full panel biochemistry laboratory safety tests (with the exception of screening and follow-up where a fasting period of 4 hours is sufficient). On Day 1, no food is permitted from 2 hours prior to dosing until 4 hours after start of the infusion. On all other days of the in-house period, standard breakfast, lunch, dinner and snack will be provided up to discharge, at the times deemed convenient by the clinical site.
- h) Intensity of adverse events will be graded on a five-point scale (Grade 1, Grade 2, Grade 3, Grade 4 and Grade 5) based on the NCI CTCAE (v5), which can be found at:
https://ctep.cancer.gov/protocoldevelopment/electronic_applications/docs/CTCAE_v5_Quick_Reference_8.5x11.pdf
- i) The Sponsor may decide to terminate PK sampling earlier and/or timing of PK sampling may be modified based on emerging PK data (e.g., consecutive postdose PK samples with below the limit of quantification [BLQ] concentration).
- j) Respiratory rate to be measured after the participant has rested in a supine position for at least 5 minutes.

█ [REDACTED]

█ [REDACTED]

[REDACTED]

█ [REDACTED]

- o) Participants will be randomized to two subgroups per dose group. One subgroup will have the CSF sampling on Day 3, the other subgroup on Day 5. The safety biomarker (blood) and coagulation sample will be taken accordingly.
- p) In case of ADA positive results at follow-up visit, the participant will be asked to come back to the unit monthly for additional ADA testing until *this is no longer clinically indicated (see Section 8.7)*. At each visit a corresponding PK sample must be also taken.

Table 1 Overall Schedule of Activities (cont.)

■	[REDACTED]
■	[REDACTED]
■	[REDACTED]
■	[REDACTED]
■	[REDACTED]

Table 2 Specific Schedule of Assessments

Procedure	Day -2	Day -1	Day 1												Day 2
			Nominal Time												

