			- 2 h	Predose	0 h	0.25 h	0.5 h	1 h	2 h	3 h	4 h	6 h	8 h	12 h	24 h
Standard Meals ^a	✓	✓	✓								✓		✓		✓
Alcohol Test	✓														
Drugs of Abuse	✓														
Medication History	✓														
Physical Examination ^h	✓														
Inclusion/Exclusion Criteria	✓														
12-lead ECGs ^{b,e}	✓		✓ ^c					✓	✓		✓		✓	✓	✓
Vital signs ^{d,e}	✓			✓			✓	✓	✓		✓		✓	✓	✓
Respiratory rate ^{e,g}	✓			✓			✓		✓		✓		✓		✓
Neurological Examination	✓			✓							✓			✓	✓
Cerebral spinal fluid (CSF) ^j		✓													
Coagulation	✓														
Pharmacokinetic Sampling (Blood) ^e				✓		✓	✓	✓	✓	✓	✓	✓	✓	✓	✓
Anti-RO7126209 Antibodies				✓											
Full hematology and full blood chemistry	✓														✓
Urinalysis ^f	✓														✓

Procedure	Day -2	Day -1	Day 1											Day 2	
			Nominal Time												
			- 2 h	Predose	0 h	0.25 h	0.5 h	1 h	2 h	3 h	4 h	6 h	8 h	12 h	24 h
Drug Administration					✓										

- a) Participants will have to be fasted (water consumption is permitted) for at least 10 hours prior to full panel biochemistry laboratory safety tests (with the exception of screening and follow-up where a fasting period of 4 hours is sufficient. No food is permitted from 2 hours prior to dosing until 4 hours after start of the infusion on Day 1. On all other days of the in-house period, standard breakfast, lunch, dinner and snack will be provided at the times deemed convenient by the site.
- b) Triplicate 12-lead ECGs (within 5 minutes) will be measured after the participant has rested in a supine position for at least 10 minutes.
- c) Three triplicate ECGs (9 in total) will be recorded within 1 hour prior to breakfast (at least 2 hours prior to dosing) and used as the baseline time point.
- d) Includes single measurements of blood pressure (systolic and diastolic), pulse rate and body temperature. All measurements to be taken after the participant has rested in a supine position for at least 5 minutes.
- e) Order of Assessments: (1) ECGs; (2) Vital signs; (3) Respiratory Rate; (4) PK blood sampling; (5) Laboratory safety tests and other blood sampling (anti-RO7126209 antibodies).
- f) Dipstick analysis of protein, blood, glucose, pH and leukocytes.
- g) Respiratory rate to be measured after the participant has rested in a supine position for at least 5 minutes.
- h) Abbreviated physical examinations (including weight).

i) [Redacted]

[Redacted]

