4.1.2 Treatment Groups

The following tentative dose levels are planned:

- Dose level 1: 0.1 mg/kg RO7126209 or matching placebo
- Dose level 2: 0.3 mg/kg RO7126209 or matching placebo
- Dose level 3: 0.9 mg/kg RO7126209 or matching placebo
- Dose level 4: 2.7 mg/kg RO7126209 or matching placebo
- Dose level 5: 5.4 mg/kg RO7126209 or matching placebo

The dose levels are tentative, and may be revised based on emerging data. Higher doses than planned may be administered provided that all the dose escalation increments and stopping rules are followed. [REDACTED]

[REDACTED] with a maximum of 60 participants enrolled in the study.

If the safety data (AEs, ECGs, vital signs, laboratory safety tests, [REDACTED] assessments) of the first 48 hours following intravenous administration of RO7126209 or placebo is acceptable based on the judgment of the Investigator, the remaining participants will be dosed [REDACTED] after the first dosing occasion.

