8.3 ADVERSE EVENTS AND SERIOUS ADVERSE EVENTS

The definitions of an AE or serious adverse event (SAE) can be found in [Appendix 2](#). The non-serious adverse events of special interest and disease-related events and/or disease-related outcomes not qualifying as AEs or SAEs are discussed in Sections [8.3.6](#) and Section [8.3.7](#).

The Investigator and any qualified designees are responsible for ensuring that all adverse events (including assessment of seriousness, severity and causality; see [Appendix 2](#)) are recorded on the Adverse Event eCRF and reported to the Sponsor in accordance with instructions provided in this section and in [Appendix 2](#).

Procedures used for recording adverse events are provided in [Appendix 3](#).

8.3.1 Time Period and Frequency for Collecting Adverse Event and Serious Adverse Event Information

The method of recording, evaluating, and assessing causality of AEs and SAEs and the procedures for completing and transmitting SAE reports are provided in [Appendix 2](#).

Clinic staff will seek information on adverse events at each study day. All adverse events, whether reported by the participant or noted by study personnel, will be recorded in the participant's medical record and on the Adverse Event eCRF as follows:

After informed consent has been obtained **but prior to initiation of study treatment**, all adverse events caused by a protocol-mandated intervention should be reported (e.g., adverse events related to invasive procedures such as lumbar puncture). If the adverse event meets the criteria for serious adverse event (see Section 2 from [Appendix 2](#)), it should be reported immediately.

After initiation of study treatment, all adverse events, regardless of relationship to study treatment, will be reported until the last follow-up visit (57 ± 4 days after dosing).

Post-study adverse events and serious adverse events: The Investigator is not required to actively monitor participants for adverse events after the end of the adverse event reporting period of 57 days ± 4 days after dosing.

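### The assessment order in Section 8.10.1, read literally, puts the 48-hour neurological examination after a same-day lumbar puncture in one CSF subgroup only, which blurs attribution at sentinel and single-cohort decisions

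*Combined protocol and SAP*

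**What the plan says.** Section 8.10.1 sets the sequence for time points with more than one assessment: ECGs, vital signs, respiratory rate and PK blood, then "5) Laboratory safety tests and other blood sampling (anti-RO7126209 antibodies); (6) CSF sampling; (7) others". The neurological examination is not named. Note e to Table 2 repeats the sequence only as far as the blood samples ("Order of Assessments: (1) ECGs; (2) Vital signs; (3) Respiratory Rate; (4) PK blood sampling; (5) Laboratory safety tests and other blood sampling") and mentions neither CSF sampling nor the neurological examination.

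In Table 1, the row "Neurological Examination" is marked at screening and on Days -2, 1, 2, 3, 4, 6, 8, 15, 29 and 57. The row "Cerebral spinal fluid" is marked on Day -1, Day 3 and Day 5. Note o says that CSF subgroups are randomized within each dose group and adds: "One subgroup will have the CSF sampling on Day 3, the other subgroup on Day 5".

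Three other places bear on the consequences:
- Section 8.3.1 gives, as an example of events caused by protocol procedures, "adverse events related to invasive procedures such as lumbar puncture".
- Section 4.1.2 releases the rest of a cohort if the sentinel safety data "of the first 48 hours following intravenous administration of RO7126209 or placebo is acceptable based on the judgment of the Investigator". The synopsis describes the sentinel pair as one active and one placebo.
- Section 9.3.4 defines a DLE as a treatment-related reaction within 8 days that would rule out giving the same dose again.

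**The concern.** The product is designed to reach the brain, so neurological signs matter among its safety signals, and lumbar puncture is a recognized source of adverse events in this protocol. When the examination follows the puncture, a new sign has two candidate causes. Blaming the puncture can hide a drug effect. Blaming the drug can create a treatment-related event or a DLE that does not exist.

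Day 3 is also the last scheduled neurological examination inside the 48-hour sentinel window. The two sentinels may then be examined under different conditions just before the decision to dose the rest of the cohort.

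**Working it through.** **1. Where the two procedures meet.** CSF days are -1, 3 and 5. Examination days near dosing are -2, 1, 2, 3, 4, 6 and 8. The only shared day is Day 3. Section 8.10.1 leaves the examination no category except its last one, after CSF sampling. The literal order therefore affects one examination, at 48 hours, in one subgroup.

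**2. Cohort sizes.** Section 9.1 gives 4 active + 2 placebo at levels 1 and 2, and 6 + 2 at levels 3 to 5. The total is 2 × 6 + 3 × 8 = 36, which reproduces the stated enrolment (26 active, 10 placebo).

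**3. Separability when pooled.** If the CSF split is 1:1 and balanced by treatment, Day 3 gives 13 active + 5 placebo with a same-day puncture and 13 + 5 without. Treatment and puncture are crossed, so both effects can be estimated, though imprecisely. With no events observed, the exact 95% upper limits are:
- 0 of 5: 1 − 0.025^(1/5) = 52%
- 0 of 13: 1 − 0.025^(1/13) = 25%

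**4. The sentinel pair.** Assume a 1:1 split, not stratified by treatment or sentinel status. The probability that the two sentinels fall in different CSF subgroups is:
- Levels 1 and 2 (n = 6): 2 × (3/6) × (3/5) = 0.60
- Levels 3 to 5 (n = 8): 2 × (4/8) × (4/7) = 0.57
- At least one divided pair in five levels: 1 − 0.40² × 0.4286³ = 0.987

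In a divided pair, treatment and same-day puncture coincide completely at 48 hours. By symmetry, the active sentinel is the one punctured in half of these cases (0.30 or 0.29 per level).

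**5. One cohort.** Under the same assumption, both placebo participants of a cohort fall in the same CSF subgroup with probability 1 − 0.60 = 0.40 or 1 − 0.57 = 0.43. One subgroup then has no placebo participant.

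**6. Effect of one misattributed DLE.** I used the Appendix 6 model, logit(p) = α + β log(dose/D_ref), with the printed bivariate normal prior for (α, log β), D_ref read as 0.3 mg/kg, the printed dose grid and the criterion Prob(DLE rate ≥ 30%) < 0.2. The posterior was integrated numerically.
- *Plan's own figures.* Appendix 6 simulates 4 active at each of the first three levels. With 0/4 and 0/4 at the first two levels and 1, 2 or 3 DLEs in 4 at 0.9 mg/kg, the highest allowed doses are 1.2, 0.6 and 0.4 mg/kg, as printed in Appendix 6 Table 1. With no DLE the safety limit exceeds 2.7, and the table prints 2.7, the tripling step.
- *Planned sizes (4, 4, 6 active).* With 0/6 at 0.9 mg/kg the safety limit is 5.4 mg/kg, so the step to 2.7 governs. With 1/6 the limit is 1.8 mg/kg (probability 0.179 at 1.8 and 0.210 at 2.1).

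The next-dose contrast is therefore 2.7 versus 1.8 mg/kg at planned sizes, or 2.7 versus 1.2 as printed for cohorts of 4 active. The exposure limit in Section 9.3.4 is not included, because its value is not visible.

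**The case against.** The strongest reply is that the design already separates the two effects. CSF subgroups are randomized within dose groups, every dose group has concurrent placebo, and note o makes no exception for placebo. Active can be compared with placebo among those punctured on Day 3, and Day 3 with Day 5 among actives. This stands. A reader might infer that procedure effects cannot be told from drug effects anywhere in the trial, and the documents do not support that. But pooling comes too late for sentinel release and cohort escalation, which rest on one or two placebo participants.

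Other points also stand:
- One might infer that only the Day 3 subgroup has had a puncture by 48 hours. Table 1 shows CSF sampling on Day -1 with no visible subgroup split, so only the same-day puncture differs.
- Reordering leaves the Day 4 examination a day after puncture in one subgroup and Day 6 a day after puncture in the other. Both fall inside the DLE window.
- One might set the model's limits of 5.4 and 1.8 mg/kg side by side as the change in next dose. Section 9.3.4 uses the model limit only when it is below the default increment, so 5.4 would not be the next dose.
- A puncture sign becomes a DLE only if it is misjudged both as treatment-related and as ruling out the same dose again. Clinical judgment also overrides the model. No probability can be put on this chain.
- The sequence applies where applicable, and placing the examination in the catch-all is an inference, although no other category is offered.
- A safety subsection, several Table 1 notes and one item of the sentinel review list are redacted and may settle the timing.

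**Conclusion.** The point holds in a limited form. On the visible text, Section 8.10.1 with Table 1 and note o puts the 48-hour neurological examination after a same-day lumbar puncture in one CSF subgroup and not the other. This does not undermine the pooled safety comparison. It does weaken attribution where the numbers are smallest: the sentinel pair at 48 hours and the single cohort.

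The chance of a divided sentinel pair, 0.57 to 0.60 per level, depends on an unstated 1:1 split without stratification. The possible shift in the model's next dose, 2.7 to 1.8 mg/kg, depends on planned cohort sizes, D_ref read as 0.3 mg/kg and a misjudged DLE, and remains subject to clinical override. It shows how sensitive the model is to one event; it is not an expected loss. The case for acting is that the ambiguity is avoidable at no cost.

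**What to change.** In Section 8.10.1, list the neurological examination as its own step before CSF sampling, unless redacted text already fixes that order. On Day 3 every participant would then have the 48-hour examination without a same-day puncture. The change is one line in the protocol and the site worksheet. It adds no procedure, visit or participant, and enrolment stays at 36.

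It would also help to state the CSF allocation ratio and whether it is stratified by treatment, since the pooled separation of effects relies on that balance.

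The reordering does not remove carry-over from the Day -1 puncture, or the difference between subgroups at the Day 4 and Day 6 examinations. Findings there still need to be read with the puncture day in view.
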